6. ASSESSMENT AND FOLLOW-UP	13
7. STATISTICS AND DATA ANALYSIS	13
8. REGULATORY ISSUES	15
8.1. Ethics approval	15
8.2. Consent	15
8.3. Confidentiality	16
8.4. Indemnity	16
8.5. Sponsor	16
8.6. Funding	16
8.7. Audits	16
9. STUDY MANAGEMENT	16
10. PUBLICATION POLICY	16
11. References	17

Glossary of Abbreviations

Abbreviation	Definition
ECG	Electrocardiogram
AF	Atrial fibrillation
pAF	Paroxysmal atrial fibrillation
PsAF	Persistent atrial fibrillation
ECGI	Electrocardiographic imaging
DCCV	Direct current cardioversion

Keywords

atrial fibrillation, ablation, electrophenotype, ECGI

Study summary

TITLE	Identification of specific electrophenotypes in human atrial fibrillation – INSPECT-AF
DESIGN	Single Centre, Observational Study
AIMS	
1. Investigate the range of AF electrophenotypes and mechanisms in human AF and identify the important functional, structural and clinical determinants of the AF electrophenotype2. Develop the use of non-invasive modalities to classify the underlying AF electrophenotype
OUTCOME MEASURES	
1. Freedom from AF2. AF burden3. Quality of life
POPULATION	Patients with atrial fibrillation due to undergo first time atrial fibrillation ablation or DCCV for under clinical grounds at Hammersmith Hospital
ELIGIBILITY	Adult patients 18-85 years, who are able to give informed consent,
DURATION	4 years

1. INTRODUCTION

1.1. Background

Atrial fibrillation (AF) is the most common cardiac arrhythmia in adults(1), with an estimated prevalence of 1% and is projected to become more prevalent (2, 3). AF is also a significant source of morbidity and mortality (4, 5) as well as reduced quality of life and exercise capacity in patients with AF-related symptoms, which can be improved with maintenance of sinus rhythm (6).

Limitations of current treatments and catheter ablation for AF

Catheter ablation is a commonly used to aid maintenance of sinus rhythm. We recently reported that pulmonary vein isolation (PVI) is markedly more effective than strategies not incorporating PVI (7), and PVI therefore remains the cornerstone of AF ablation. In patients with paroxysmal AF (PAF), PVI reduces AF recurrence in around 70-80% of patients (8), however in persistent AF (PsAF) the success rate of ablation is only 50% (9). The atrial substrate is an important determinant of recurrence in PsAF, this may explain the relatively poor outcomes of a PVI-only ablation approach. A wide range of adjunctive ablation strategies have been studied, however we have shown none conclusively improve success rates (10).

Lack of consensus on AF mechanisms - absence of mechanism-directed treatments

One major issue limiting the success of treatments for PsAF is the lack of mechanism-directed therapies. Although PsAF appears to be a heterogenous entity, ablation strategies for persistent AF centre around PVI. Adjunctive strategies are largely empirical with no tailoring of strategy towards patient-specific mechanisms. The absence of mechanism-directed treatments is due partly to the lack of consensus on the electrophysiological mechanisms that sustain AF. Two broadly contradictory hypotheses have been put forward. The “anarchical” model of AF proposes that AF is sustained by multiple self-perpetuating activation wavelets propagating randomly until extinguished(11). Importantly, this model is based on an absence of localised sources and would be best treated by lines of block to confine and extinguish wavelets (12, 13). Conversely, the “hierarchical” model proposes that AF is sustained by localised drivers or ‘rotors’ that may be stable or dynamic (14-16) however multi-centre studies of rotor guided ablation has demonstrated this approach to be ineffective (17, 18).

Concept of spectrum of different ‘electrophenotypes’ of AF

Lastly, CMR has been used to quantify LA fibrosis (26), and based on our groups work in VF showing the important role of fibrosis pattern on determining VF mechanism (19), LA fibrosis maps from CMR may therefore be useful in complementing ECG and ECGI in helping to classify an individual's AF mechanism and electrophenotype. Our own analyses have described the distribution of scar within the left atrium and the effect of fibrosis on left atrial electrophysiological properties, with recent demonstrations that LA fibrosis as detected on CMR correlates with intracardiac electrograms voltage acquired in atrial fibrillation (27).

Recurrence of atrial arrhythmia after AF ablation

Current success rates following ablation for PsAF are only 50%. A significant proportion of these recurrences are due to the organised atrial arrhythmias atrial flutter and atrial tachycardia. Atrial flutter may be cavotricuspid isthmus (CTI) dependent or have a different mechanism. Ablation for CTI dependent flutter has a significantly higher success rate compared to ablation for atrial tachycardia. Additionally, knowledge of the tachycardia mechanism can be helpful to plan an ablation procedure; if the tachycardia originates in the right atrium the procedure can be undertaken under local anaesthetic without a transeptal puncture, while a left atrial tachycardia may require a general anaesthetic and transoesophageal echocardiography for transeptal puncture.

Biomarkers for atrial fibrillation

Proteomics profiling has been used to identify proteins independently associated with incident AF (28). MicroRNAs have similarly been associated with incident AF and cardiac remodelling (29). Machine learning (ML) has been incorporated with proteomics to yield new insights and outperform traditional techniques (30).

1.2. Rationale for current study

1. In human AF, there is a spectrum of different AF mechanisms (manifest as a

- spectrum of 'electrophenotypes') that can sustain AF
2. The specific AF electrophenotype in each patient is determined by the underlying atrial substrate, and correlates to functional (e.g. conduction velocity), structural (fibrosis burden) and clinical characteristics (e.g. AF duration)
 3. Analysis of surface ECGs, 252 lead ECGs and scar maps from MRI, in isolation or in combination, can provide an accurate non-invasive classification of AF electrophenotype, when compared to the gold-standard classification using intracardiac electrograms
 4. Machine learning (ML) can be applied to ECGs, electrograms, 252 lead ECG and cardiac MRI to aid classification of electrophenotype

2. STUDY OBJECTIVES

Primary objectives

1. Investigate the range of AF electrophenotypes and mechanisms in human AF and identify the important functional, structural and clinical determinants of the AF electrophenotype

Secondary objectives

2. Develop the use of non-invasive modalities such as the surface ECG, 252 lead ECG and CMR, in isolation or in combination, to classify the underlying AF mechanism/electrophenotype

3. STUDY DESIGN

This is a prospective interventional study investigating invasive and non-invasive tools for determining AF electrophenotype. The study will last 2 years in duration and will recruit patients undergoing ablation or DCCV procedures for atrial fibrillation (AF). Patients will be recruited from secondary care clinics or pre-assessment prior to procedures at Hammersmith Hospital.

The study will be run at a single centre at the Hammersmith Hospital, Imperial College Healthcare NHS Trust. We will aim to enrol 300 patients.

3.1. Study outcome measures

We will classify patients into electrophenotypes based on the invasive and non-invasive data collected. The primary outcome measure will be freedom from AF. Secondary outcome measures will be AF burden and quality of life.

[figure not shown]

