7. STATISTICS AND DATA ANALYSIS

We will use the data collected to investigate the specific determinants of AF mechanism and electrophenotype. Patients will be classified into a range of AF mechanisms and electrophenotypes, ranging from organised AF sustained by localised drivers through to disorganised AF. The specific functional (e.g. atrial

conduction properties), structural (e.g. left atrial fibrosis burden) and clinical (e.g. AF duration) determinants of the AF electrophenotype will be investigated.

Intracardiac EGM data and 252 lead ECG

The 252 electrode device data will be analysed using a combination of established signal processing (dominant frequency, phase mapping and Shannon entropy) and machine learning techniques (unsupervised learning to cluster data into distinct phenogroups. For the subset of 10 patients with MRI data, we apply our 'in house' inverse solution and Tikhonov regularisation steps to reconstruct the epicardial electrograms.

Cardiac MRI

I will analyse burden of fibrosis and fibrosis distribution patterns and correlate these with the electrogram data.

AF electrophenotype will be determined using the analyses above. I will characterise each patient using both a regional and a global approach. The regional approach will analyse each sequentially collected 'kernel' of data from the RA and LA and assign a metric of organisation. The electrophenotype of a single patient therefore will be described by the number of organised/disorganised sites. The global approach will assign a global metric of organisation, including data from all collected kernels from both RA and LA. I will investigate the determinants of electrophenotype by correlating electrophenotype with clinical parameters including AF duration, co-morbidities and left atrial size on echocardiography. I will also compare intracardiac mapping pre- and post- PVI to investigate the impact of PVI on AF electrophenotype. I will investigate the degree to which the AF electrophenotype can predict outcomes compared to conventional clinical and echocardiographic predictors.

Biomarkers for identification of AF electrophenotype

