We will look for differences in lipid metabolite levels, miRNA and protein expression between the electrophenotype groups, which may serve as biomarkers to non-invasively distinguish between these groups. I will analyse human serum using DNA barcode technology integrated with a nanopore platform to measure levels of these circulating miRNAs and proteins. Machine learning has been used effectively in proteomic studies (30). I aim to apply the biomarker data with electrical and imaging data using unsupervised machine learning to identify clinically relevant clusters (phenotypes).

Developing non-invasive methods to classify AF electrophenotype

Using simultaneously collected 252 lead ECG and intracardiac data, together with CMR LA fibrosis data, the surface ECG and biomarkers, I will develop tools to non-invasively classify AF electrophenotype.

Using the intracardiac data as the gold standard, I will continue to develop tools to determine the degree of global fibrillation organisation from surface ECGs, using band-power feature analysis and machine learning techniques. 252 lead ECG-derived biatrial maps in atrial fibrillation will then be analysed using both established (dominant frequency, phase mapping and Shannon entropy) and the novel (ML based analysis, including unsupervised machine learning) to further stratify patients into a spectrum of organised to disorganised electrophenotypes. Simultaneous

intracardiac and 252 lead ECG recordings will also allow further validation of 252 lead ECG in atrial fibrillation. I will use CMR data to correlate electrophenotype with anatomical data. LA fibrosis will be categorised by both degree and distribution of fibrosis and correlated with both intracardiac and non-invasively acquired electroanatomical data using linear regression models and ML. Invasive and non-invasive parameters will be combined and correlated with AF recurrence to create a tool using only non-invasive data to determine a patient-specific electrophenotype.

Outcomes

Freedom from AF, AF burden and quality of life outcome data will be correlated with electrophenotype groups (as defined by the above analyses) to investigate if certain groups benefit more from ablation than others.

Sample size is based on collecting sufficient data to detect differences in electrophenotypes using biomarkers and ECG parameters.

Data will be analysed by the chief investigator and the research team at the National Heart and Lung Institute, Imperial College London.

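### The reference electrophenotype is defined inconsistently: on one reading it contains the non-invasive tests to be judged against it, and tool-derived groups could be tested against the recurrence that shaped them

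*Combined protocol and SAP*

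**What the plan says.** The combined protocol and SAP describes the electrophenotype label in several ways.

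- **Intracardiac reference.** Section 1.2 expects non-invasive classification to be accurate "when compared to the gold-standard classification using intracardiac electrograms". Section 7, on developing non-invasive methods, repeats this: "Using the intracardiac data as the gold standard". The regional and global organisation metrics in section 7 are built from atrial kernels, the global one "including data from all collected kernels from both RA and LA".
- **Mixed label.** Section 3.1 says "We will classify patients into electrophenotypes based on the invasive and non-invasive data collected". Section 7 says "AF electrophenotype will be determined using the analyses above", directly after the paragraphs on intracardiac and 252-lead data and on cardiac MRI. Later in section 7, 252-lead maps are also used to place patients along the range from organised to disorganised.
- **Multimodal clusters.** Section 7, on biomarkers: "I aim to apply the biomarker data with electrical and imaging data using unsupervised machine learning". The resulting clusters are also called phenotypes.
- **Recurrence.** Section 7: "Invasive and non-invasive parameters will be combined and correlated with AF recurrence to create a tool using only non-invasive data". The tool's output is a patient-specific electrophenotype. The Outcomes paragraph then correlates freedom from AF, AF burden and quality of life with electrophenotype groups, defined only by reference back to the preceding analyses. Freedom from AF is the primary outcome measure in section 3.1.

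The plan describes no hold-out set, cross-validation, blinded assignment of the reference or locking of the label. In section 3.2, intracardiac mapping is listed for ablation patients only; DCCV patients have surface recordings.

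**The concern.** An accuracy study needs a reference that is independent of the test it judges. If 252-lead or MRI data help to set the label, each agrees with the label partly because it agrees with itself. The same applies to left atrial fibrosis, which section 7 names as a structural determinant of the electrophenotype although MRI is among the analyses that precede the label.

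The recurrence question is a different one. Groups shaped by recurrence will differ in recurrence in the patients used to shape them, whether or not the electrophenotype carries prognostic information.

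At stake are the secondary objective (non-invasive classification), the fibrosis part of the primary objective, and the analysis of whether some groups benefit more from ablation. An analyst could follow either definition and still comply with the plan, so a reader of the results could not tell which one produced them.

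**Working it through.** **Plan's own figure.** There is none to reproduce. No accuracy, sensitivity, specificity or AUC is stated. The target of 300 patients comes without alpha, power, effect size or variance, so it cannot be checked. The calculations below show direction and possible size under assumptions.

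**1. Test data inside the label**

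Assumptions, none from the documents: intracardiac score I and non-invasive score N are standard normal with correlation ρ. The label is the median split of (1−w)·I + w·N, where w is the weight given to the non-invasive data. The test is the median split of N.

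- Correlation of test score with label score: r = [(1−w)ρ + w] / √[(1−w)² + w² + 2w(1−w)ρ]
- Agreement = 1/2 + arcsin(r)/π

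With ρ = 0:
- w = 0: r = 0, agreement 50%.
- w = 0.25: r = 0.25/√(0.5625 + 0.0625) = 0.316, agreement 0.5 + 0.322/3.142 = 60.2%.
- w = 0.5: r = 0.5/√0.5 = 0.707, agreement 0.5 + 0.25 = 75.0%.

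| True correlation ρ | Intracardiac only (w = 0) | w = 0.25 | w = 0.5 |
|---|---|---|---|
| 0 | 50.0% | 60.2% | 75.0% |
| 0.3 | 59.7% | 68.7% | 79.8% |
| 0.5 | 66.7% | 74.4% | 83.3% |
| 0.7 | 74.7% | 80.8% | 87.3% |

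A simulation of 400,000 draws at ρ = 0 and 0.5 agreed with the formula to within 0.001. In every row, agreement rises as soon as the non-invasive data carry weight. With the intracardiac-only label the excess is zero.

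**2. Recurrence used to form groups, then tested**

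Assumptions: 100 patients (the top of the 50–100 range for the 252-lead subgroup in section 3.2); 50% success (the figure section 1.1 gives for persistent AF); features with no relation to outcome; a linear score fitted to recurrence and split at its median; a two-sided 5% test; 2,000 runs. The feature counts are assumed.

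| Null features | False positives, same patients | False positives, new patients | Mean spurious difference in success, same patients |
|---|---|---|---|
| 5 | 42% | 5.7% | 17.5 points |
| 10 | 78% | 5.7% | 25.2 points |
| 20 | 99% | 5.3% | 37.9 points |

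Enlarging the sample does not cure this: with 300 patients the same-patient rates are 40%, 75% and 98%.

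**3. How far each problem reaches**

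- MRI is planned for 10–30 patients (section 3.2; section 7 mentions 10), at most 30/300 = 10% of enrolment. Any MRI contribution to the label, and any circular fibrosis association, is confined to them.
- AF duration, co-morbidities and left atrial size on echocardiography are not label inputs on any reading, so their association with the label is not circular.
- The comparison before and after pulmonary vein isolation uses intracardiac mapping only and is also unaffected by the inclusion of the index tests.
- DCCV patients have no listed mapping, so any label they receive rests on non-invasive data.

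**The case against.** The strongest reply is that the operational text already points to an intracardiac label. The gold standard is named twice, and the only metrics section 7 specifies come from right and left atrial kernels, which read as catheter mapping. The sentence in section 3.1 may mean only that patients are classified by invasive tools and, separately, by non-invasive ones, which fits section 3's description of the study as investigating both kinds of tool. MRI is mostly treated as something to correlate with electrogram data. On this reading the comparison contains no incorporation bias. All of that stands, and it makes the problem conditional. It does not settle which definition governs, because section 3.1 and the sentence in section 7 that follows the MRI paragraph remain in force.

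Two further points also stand. Section 7 compares biomarkers between electrophenotype groups and separately plans multimodal clusters; a reader might infer that biomarkers will be tested between clusters they helped to form, but the plan does not say so. A reader might also infer that recurrence enters the reference label itself. The text puts it in the construction of the non-invasive tool, and correlating outcome with an intracardiac label fixed beforehand would not be circular. What the plan lacks is a statement that the Outcomes analysis uses that label and not the tool's.

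Finally, the weights, correlations and feature counts above are assumed. That is correct, and the tables should be read only as illustrations.

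**Conclusion.** The concern holds as an inconsistency in the reference standard with conditional bias. If the mixed definition is followed, non-invasive accuracy, and the fibrosis association in the 10–30 MRI patients, would be biased upward. The illustrated rise for an unrelated metric is from 50% to about 60% or 75%, depending on an assumed weight, and it vanishes if the label is intracardiac only. If tool-derived groups are tested on freedom from AF in the patients whose recurrence helped to create the tool, that association is circular.

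Two stronger readings are tempting and are not supported. One is that reported accuracy is inflated by construction: the documents also name an intracardiac gold standard and claim no accuracy figure. The other is that neither objective can be answered: the clinical determinants and the comparison around pulmonary vein isolation are not affected by inclusion of the index tests, and an intracardiac label would leave the non-invasive comparison free of that bias. Clarification is still needed before analysis, because both objectives and the outcome analysis depend on this label.

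**What to change.** In section 3.1 and section 7:

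1. Define the reference electrophenotype from intracardiac mapping only. Both the regional and the global metric may stay, since both are intracardiac. Compute and lock it blind to 252-lead ECG, MRI, biomarkers and follow-up.
2. Assess non-invasive accuracy only in ablation patients with mapping, using cross-validated or held-out predictions.
3. Train the non-invasive tool on the locked label, without AF recurrence. Relate its out-of-sample prediction to recurrence as a separate step.
4. State in the Outcomes paragraph which label defines the groups.
5. Report multimodal unsupervised clusters as exploratory, and do not test a variable between clusters it helped to form.
6. Describe DCCV patients as having a predicted phenotype only.

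The cost is a change of wording and of the order of analysis, with no new data. Reported accuracy may be lower, and DCCV patients will not contribute to the accuracy estimate.

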3.2. Study protocol

Patients that suffer from AF and have been put forward for an ablation or DCCV, on clinical grounds as per current guidelines, will be recruited. Patients will be approached by a member of the clinical team by telephone from the Hammersmith Hospital waiting lists to discuss their interest in participating in the study. If the patient is interested, they will be provided with a patient information sheet, detailing information with regards to the study. The Investigators will subsequently consult with these patients to explain the study in greater detail and answer any further questions, in person, during an outpatient clinic visit or by phone. The consent form will include all information about the study and the mapping procedure.

All patient clinical data will be collected on a standardised electronic case report form.

Study groups

Diagram summarising study subgroups:

Biomarker protocol (all groups):

All patients will have blood samples taken to investigate for biomarkers that may correlate with electrophenotypes. In most cases this will be taken during the same blood draw as blood tests taken for clinical care or from sheaths in central veins that are placed routinely during an AF ablation. Rarely it may be necessary to perform an additional venepuncture in order to obtain the samples.

252 lead ECG protocol (green + orange groups):

A subgroup of 50-100 patients with persistent AF will have a 252 lead ECG. This will consist of up to 252 electrodes attached to the patient's front and back. A recording of up to 10 minutes will be taken before the AF ablation or DCCV procedure.

MRI protocol (orange group):

A subgroup of 10-30 patients who are undergoing ablation will undergo thoracic and cardiac MRI including administration of gadolinium intravenously. This will be performed on the day of their ablation procedure, prior to the ablation. This subgroup will have an additional 1-2 visits 1-2 weeks apart prior to their procedure date, where they will attend the hospital for 10 minutes of data collection with the 252 electrode device. This subgroup will have co-registration of the 252 electrode recordings taken on the day of the ablation with the MRI to allow reconstruction of the epicardial

electrograms through the inverse solution and Tikhonov regularisation steps.

DCCV protocol

1. All patients will have up to 252 electrodes placed on their chest and back **2. Surface electrical data will be collected before the procedure and removed prior to the DCCV**

2. All patients will have sedation delivered by an Anaesthetist
3. Up to 3 synchronised shocks will be delivered in accordance with routine clinical practice
4. Patient recovery

AF ablation protocol

The AF ablation procedure will take place in the electrophysiology laboratory. The procedure routinely takes place under general anaesthetic. The procedure typically lasts 2-3 hours.

1. All patients will have up to 252 electrodes placed on their chest and back, with gaps where necessary for patches/electrodes for clinical use

2. Surface electrical data will be collected throughout the procedure from the multiple electrodes

3. A subgroup of patients will have thoracic and cardiac MRI with gadolinium contrast

4. All patients will be out under general anaesthetic by a Consultant Anaesthetist.

5. All patients will have a Transoesophageal echocardiogram to exclude LAA thrombus.

6. All patients have sheaths (small plastic tubes) inserted through their groin veins (femoral veins).

7. A transseptal puncture will be performed to gain access to the left atrium under heparin cover.

8. Cardiac ablation and mapping catheters (small plastic tubes with electrodes at the end) are advanced into the heart under fluoroscopic guidance.

9. A 3D model of the heart will be created to help guide ablation using clinical software (Ensite Precision, Abbott UK or CARTO, Biosense Webster).

10. Electrical mapping data will be collected while the patient is in AF using a dedicated mapping catheter (Lasso or AFocusII/HD grid)

11. Adenosine will be administered through a central venous sheath to induce transient AV block, during which surface electrical data will be collected

12. Pulmonary Vein Isolation ablation with radiofrequency energy will be completed as per standard of care.

13. Electrical mapping data will be collected after pulmonary vein isolation if the patient has remained in AF.

14. All patients will be cardioverted as part of the standard of care.

15. Heparin reversal with Protamine.

16. Sheath removal

17. End of procedure

18. Patient recovery

Steps in bold above will be additional to the standard of care.

After the procedure has finished and all devices have been removed from the patient, we will export each patient's pseudonymised data for further offline analysis

Patients undergoing AF ablation will be provided with an AliveCor device to use up to once per day and when they have symptoms to accurately monitor for recurrence of AF. They will also have holter monitoring and clinical follow up in line with routine clinical care. Patient's will be asked to complete symptom score/quality of life questionnaires up to once per month during follow up.

Patients undergoing DCCV will be followed as per routine clinical care.

Study participation will conclude after 300 patients have been recruited. Patients will be able to leave the study at any time they wish; they need only inform the research team.

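### Biomarker blood may be drawn by different routes and at any stage of an ablation, with nothing recorded or adjusted for, so biomarker clusters can reflect sampling conditions instead of electrophenotype

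*Combined protocol and SAP*

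**What the plan says.** The biomarker protocol in section 3.2 applies to every participant: "All patients will have blood samples taken to investigate for biomarkers that may correlate with electrophenotypes". It offers three routes. The sample may be "taken during the same blood draw as blood tests taken for clinical care", or it may come "from sheaths in central veins that are placed routinely during an AF ablation". Failing both, "Rarely it may be necessary to perform an additional venepuncture in order to obtain the samples". No route has a time point, and none is placed in order relative to any drug or procedural step.

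The AF ablation protocol in the same section shows how wide the sheath window is. General anaesthesia is step 4 and sheath insertion step 6. Step 7 reads "A transseptal puncture will be performed to gain access to the left atrium under heparin cover". Adenosine follows at step 11, radiofrequency pulmonary vein isolation at step 12, cardioversion at step 14, protamine at step 15 and sheath removal at step 16. MRI-subgroup patients receive gadolinium earlier the same day. The DCCV protocol lists sedation and shocks, but no sheath, heparin or adenosine.

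Section 7 sets out two uses of the samples: "We will look for differences in lipid metabolite levels, miRNA and protein expression between the electrophenotype groups", and "I aim to apply the biomarker data with electrical and imaging data using unsupervised machine learning to identify clinically relevant clusters (phenotypes". Section 3.2 mentions a standardised electronic case report form but does not list its fields.

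**The concern.** A sheath sample taken before heparin and one taken after ablation and protamine both comply with the protocol, and so does a peripheral sample taken on another day. All enter the same analyses. General knowledge, not the documents, suggests that heparin, tissue injury from ablation or shocks, and sampling site could alter the analytes or their assay. If they do, two things are at stake.

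- **Clustering.** An unsupervised method has no label telling it to ignore a procedural shift. A shift shared by several markers can form a cluster without any imbalance between electrophenotypes. If DCCV and ablation patients are pooled, that cluster would also line up with procedure type.
- **Group comparison.** Mixed exposure adds variance. If the mix differs between electrophenotype groups, it also adds bias.

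Exposure that was not recorded at the time of the draw may not be recoverable later.

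**Working it through.** **The plan's own figure.** Section 3 gives 300 patients. Section 7 says the size rests on detecting differences using biomarkers and ECG parameters, but gives no alpha, power, effect size, SD or group sizes. The 300 therefore cannot be reproduced. Apart from that total, every input below is an assumption.

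**1. Clustering.** Assumed inputs: 300 patients, 150 of them ablations; 30 independent markers with SD 1; 6 markers carry a 1-SD difference between two equally common phenotypes; a separate set of markers shifts in exposed patients; exposure is independent of phenotype. Two-cluster k-means was run with 100 replicates per setting. The table gives the mean adjusted Rand index (0 = chance, 1 = perfect).

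| Shifted markers | Shift (SD) | Ablations exposed | With phenotype | With exposure |
|---|---|---|---|---|
| none | 0 | 70% | 0.57 | 0.00 |
| 10 | 0.5 | 70% | 0.56 | 0.00 |
| 10 | 0.75 | 70% | 0.46 | 0.09 |
| 10 | 1 | 70% | 0.00 | 0.74 |
| 10 | 1.5 | 70% | 0.00 | 0.96 |
| 6 | 1 | 70% | 0.36 | 0.18 |
| 3 | 1 | 70% | 0.57 | 0.00 |
| 10 | 1 | 20% | 0.55 | 0.00 |
| 10 | 1.5 | 20% | 0.09–0.16 | 0.58–0.69 |

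Repeat runs agree to about 0.02, except near the threshold, where they differ by up to about 0.1. Dropping the DCCV patients does not remove the effect: with 150 ablation patients, half exposed, and a 1-SD shift in 10 markers, the figures are 0.01 with phenotype and 0.71–0.74 with exposure.

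**2. Group comparison, unequal mix.** There is no true difference, n patients per group, shift d, and exposed shares p₁ and p₂. The test statistic has mean

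λ = d(p₂ − p₁) / √{[2 + d²(p₁(1−p₁) + p₂(1−p₂))]/n}

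and the type I error is Φ(−1.96 + λ) + Φ(−1.96 − λ).

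- n = 150, d = 0.5, 30% v 70%: λ = 0.2/√(2.105/150) = 1.69, giving 39%. Simulations gave 38% to 40%. With route as a covariate they gave about 5% to 6%.
- n = 75 (only 150 ablation patients have a phenotype), otherwise the same: λ = 0.2/√(2.105/75) = 1.19, giving 22%.
- n = 150, d = 0.25, 40% v 60%: λ = 0.43, giving 7%.
- Equal mix, any d: λ = 0, giving 5%.

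**3. Group comparison, equal mix.** Only precision is lost. The effective sample size is 1/[1 + p(1−p)d²]. With p = 0.5:

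- d = 0.5: 1/1.0625 = 94%
- d = 1: 1/1.25 = 80%
- d = 2: 1/2 = 50%

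**The case against.** The strongest reply is that no harm has been shown. The documents give no size for any effect of heparin, other drugs or sampling site on these analytes, so every shift above is assumed. The clustering result is a threshold effect: clusters follow the larger signal, and exposure does not dominate at 0.5 SD, with only 3 markers affected, or at 1 SD with 20% of ablations exposed. Section 7 also clusters biomarkers together with electrical and imaging data, which the illustration leaves out and which may hold the clusters closer to electrophenotype. All of this stands. It limits the claim to what can happen.

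A reader might infer that electrophenotype comparisons are biased because DCCV patients have no sheath. The documents do not support that for groups defined by intracardiac data, which section 7 treats as the gold standard and which only ablation patients have. Bias there needs the route mix to differ by electrophenotype within ablation patients, and nothing in the documents says that it does.

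A reader might also take the clinical-care bloods to be pre-procedure. Section 3.2 does not say so; their timing is open too.

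Finally, biomarkers appear in neither the objectives (section 2) nor the outcome measures (section 3.1), and a laboratory manual may exist. However, section 7 cites biomarkers as part of the basis for the sample size, and the documents refer to no such manual.

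**Conclusion.** The point holds as a design gap. The plan expressly permits mixed routes and exposures, pools the samples, and requires no recording, standardisation or adjustment. That much is plain from the text.

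The size of the harm is conditional. If sampling conditions shift enough markers by enough, clusters can reproduce those conditions. In the illustration this occurs at about 1 SD in 10 of 30 markers with 70% of ablations exposed, and not at 0.5 SD. Comparisons within ablation patients lose precision (to 80% of the effective sample size at 1 SD with half exposed). Their type I error is inflated only if the route mix is unequal: for a 0.5-SD shift and 30% v 70%, about 39% at 150 per group or 22% at 75.

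It would go too far to conclude that the clusters will be artefacts of heparin or route. The documents contain nothing on the direction or size of such effects. The change is still worth making, because it is cheap before sampling and hard to make good afterwards.

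**What to change.** In the biomarker protocol of section 3.2:

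- Set one research sampling point before the procedure for all ablation and DCCV patients, using the clinical bloods or the separate venepuncture already allowed.
- Allow a sheath sample only as a fallback, immediately after insertion (step 6) and before heparin (step 7). Such a sample still follows general anaesthesia and, in the MRI subgroup, gadolinium, so it must be identifiable as a separate route.
- Record draw time, draw site and prior drug or contrast exposure on the eCRF.

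In section 7:

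- Adjust the biomarker group comparisons for route.
- Keep post-heparin samples for sensitivity analysis only.
- Prespecify a check that clusters do not reproduce route or procedure type.

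The cost is a short amendment and a few eCRF fields. Some samples move to sensitivity analysis, and some patients need the extra venepuncture that the protocol already permits. The change concerns research sampling only and alters no treatment.
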